Official Study Title

Biomarker Studies to Predict Treatment Outcomes of Enfortumab Vedotin in Advanced Urothelial Carcinoma

ClinicalTrials.gov Identifier (NCT Number): Pending Assignment

Document Date: June 19, 2025

Confidentiality Notice:

This document is intended for use in the ClinicalTrials.gov registration and results reporting process only. It does not contain any personal identifiers of study participants.

1. Official Study Title

Biomarker Studies to Predict Treatment Outcomes of Enfortumab Vedotin in Advanced Urothelial Carcinoma

2. Background and Rationale

Advanced urothelial carcinoma (aUC) remains a highly fatal malignancy, with limited durable responses to first-line platinum-based chemotherapy. Enfortumab vedotin (EV), a nectin-4-targeting antibody-drug conjugate, has shown promising efficacy in aUC patients, both in the first-line setting when combined with pembrolizumab and in later-line setting when used as monotherapy (EV/EVP). However, despite its clinical success, the occurrence of significant toxicities and high treatment costs highlight the need for predictive biomarkers to optimize treatment outcomes and mitigate adverse effects. Nectin-4, as the target of EV, along with ADAM10/17, enzymes responsible for nectin-4 shedding, and soluble nectin-4 (sNectin-4), have emerged as potential biomarkers for predicting EV treatment outcomes.

3. Objectives

3-1. Primary Objective

(1) To investigate the correlation between membranous nectin-4 (mNectin-4) expression and treatment outcomes in patients with aUC receiving EV/EV-P.

3-2. Secondary Objectives

(1) To evaluate the association between ADAM10/17 expression and treatment outcomes of EV/EVP in aUC.

(2) To examine the relationship between sNectin-4 levels and treatment efficacy of EV/EVP in aUC patients.

3-3. Exploratory Objective

(1) To assess whether mNectin-4, ADAM10/17, and sNectin-4 can serve as predictive biomarkers for EV/EVP in aUC patients.

4. Study Design

4-1. Study Type: Observational

4-2. Study Design: Prospective cohort study

4-3. Study Center: Single-center (National Taiwan University Hospital, NTUH); may expand to

multi-center in the future

4-4. Enrollment Method: Consecutive enrollment of eligible patients

4-5. Study Period: April 1, 2025 to December 31, 2029

4-6. Estimated Sample Size: 100 patients receiving EV/EVP, plus 100 patients treated with platinum-

based chemotherapy as a comparator cohort

5. Study Population

5-1. Inclusion Criteria

(1) Histologically confirmed diagnosis of advanced aUC, including bladder cancer or upper tract urothelial carcinoma

(2) Age \geq 20 years

(3) Received EV/EVP or first-line platinum-based chemotherapy at NTUH

- (4) Availability of archival formalin-fixed paraffin-embedded (FFPE) tumor tissue for biomarker analysis
- (5) Willingness to provide serum samples at predefined time points
- (6) Ability to provide written informed consent

5-2. Exclusion Criteria

- (1) Patients who have received prior investigational agents targeting nectin-4
- (2) Inadequate tissue samples or insufficient serum collection
- (3) Concurrent participation in another interventional clinical trial
- (4) Any condition that, in the investigator's judgment, would compromise the patient's safety or compliance with study procedures

5-3. Sampling Method

- (1) Consecutive enrollment of eligible patients meeting the inclusion criteria

5-4. Estimated Sample Size

- (1) 100 patients treated with EV/EVP
- (2) 100 patients treated with first-line platinum-based chemotherapy (for comparative biomarker analysis)

6. Study Groups/Cohorts

6-1. Group 1: EV Therapy Cohort

- (1) Population: Patients with aUC receiving EV/EVP at NTUH
- (2) Treatment: Standard EV-based regimen (monotherapy or in combination with pembrolizumab)
- (3) Biospecimen Collection:
 - Archival tumor tissue for immunohistochemistry (IHC) analysis of mNectin-4 and ADAM10/17 expression
 - Serum samples collected at predefined time points for sNectin-4 quantification via ELISA

(4) Clinical Data Collection: Demographics, disease characteristics, treatment details, response assessments (RECIST), progression-free survival, overall survival, and adverse events

6-2. Group 2: Chemotherapy Cohort (Comparator Cohort)

(1) Population: Patients with aUC who received first-line platinum-based chemotherapy at NTUH during the same enrollment period

(2) Treatment: Standard first-line cisplatin- or carboplatin-based chemotherapy

(3) Biospecimen Collection:

- Archival tumor tissue for IHC analysis of mNectin-4 and ADAM10/17
- Serum samples for sNectin-4 quantification

(4) Clinical Data Collection: As per EV therapy cohort, for comparative analysis

7. Endpoints / Outcome Measures

7-1. Primary Outcome Measure

(1) Objective Response Rate (ORR): Proportion of patients achieving complete or partial tumor response according to RECIST 1.1 criteria after enfortumab vedotin treatment. Time Frame: Up to 12 months after treatment initiation

7-2. Secondary Outcome Measure

(1) Progression-Free Survival (PFS): Time from treatment start to disease progression or death from any cause. Time Frame: Up to 24 months

(2) Overall Survival (OS): Time from treatment initiation to death from any cause. Time Frame: Up to 36 months

(3) Treatment-Related Adverse Events: Incidence and severity of adverse events graded by CTCAE v5.0

during treatment. Time Frame: Throughout treatment duration

(4) Correlation of Biomarker Expression with Treatment Outcomes: Association between mNectin-4, ADAM10/17 expression, serum sNectin-4 levels, and clinical outcomes. Time Frame: Assessed at baseline and during follow-up

8. Methods / Assessments

8-1. Sample Collection

(1) Tumor Tissue:

- Archival formalin-fixed paraffin-embedded (FFPE) tumor specimens will be retrieved from diagnostic pathology samples.
- Tumor samples will be analyzed for mNectin-4 and ADAM10/17 expression by IHC.

(2) Serum Samples:

- Blood samples will be collected at predefined time points: before the initiation of systemic therapies/at first radiographic response assessment (approximately week 6–8)/t disease progression or end of treatment
- Serum will be isolated and stored at –80°C for subsequent analysis of sNectin-4 by ELISA.

8-2. Biomarker Analysis

(1) IHC:

- FFPE tissue sections will be stained for nectin-4 and ADAM10/17 using validated antibodies.
- Expression will be semi-quantitatively scored based on H-score and/or staining intensity and proportion.

(2) Enzyme-Linked Immunosorbent Assay (ELISA):

- Serum sNectin-4 levels will be quantified using a commercially available ELISA kit following manufacturer's instructions.

8-3. Statistical Analysis

- (1) Descriptive statistics will be used to summarize patient characteristics and biomarker distributions.
- (2) Group comparisons:
 - Mann-Whitney U test or t-test for continuous variables
 - Chi-square or Fisher's exact test for categorical variables
- (3) Survival analysis:
 - Kaplan-Meier method for estimating PFS and OS
 - Log-rank test for between-group comparisons
- (4) Multivariable analysis:
 - Cox proportional hazards model to assess the independent association of biomarkers with survival outcomes
 - Logistic regression for associations with objective response

9. Ethics / Regulatory Compliance

9-1. The study protocol has been reviewed and approved by the Research Ethics Committee E of National Taiwan University Hospital.

IRB Approval Number: 202502065RINE

Approval Date: 2025-03-19

9-2. This study will be conducted in accordance with the principles of the Declaration of Helsinki, ICH Good Clinical Practice (GCP) guidelines, and applicable local regulatory requirements.

9-3. Informed consent will be obtained from all participants before enrollment. The consent process will include information on study purpose, procedures, risks, benefits, data confidentiality, and the

voluntary nature of participation.

9-4. Confidentiality and data protection:

- All personal identifying information will be coded and stored securely in password-protected databases.
- Only authorized study personnel will have access to identifiable data.
- Samples will be labeled with de-identified study codes.
- Data will be reported in aggregate to prevent the identification of individual participants.

10. Study Timeline

10-1. Planned Study Start Date: April 1, 2025

10-2. Planned Study End Date (Final Data Collection): December 31, 2029

10-3. Primary Completion Date: September 30, 2029

10-4. Study Completion Date: December 31, 2029

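### Eligibility and consent wording allow enrolment after treatment has begun, against the pre-treatment serum draw; late entrants would bias absolute OS, PFS and ORR upward

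*Protocol*

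**What the plan says.** Protocol 4-2 describes a prospective cohort, and 4-4 and 5-3 call for consecutive enrolment of eligible patients.

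Three places define who enters by treatment:
- Inclusion 5-1(3): "Received EV/EVP or first-line platinum-based chemotherapy at NTUH".
- Group 1, 6-1(1): "Patients with aUC receiving EV/EVP at NTUH".
- Group 2, 6-2(1): "Patients with aUC who received first-line platinum-based chemotherapy at NTUH during the same enrollment period".

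None of them describes a patient about to start. On consent, 9-3 says: "Informed consent will be obtained from all participants before enrollment". It does not mention the first dose.

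The outcome clocks start at treatment. PFS in 7-2(1) is "Time from treatment start to disease progression or death from any cause" and OS in 7-2(2) is "Time from treatment initiation to death from any cause". The 12-month ORR window in 7-1 also runs from treatment initiation.

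The first two serum draws in 8-1(2) are "before the initiation of systemic therapies/at first radiographic response assessment". Inclusion 5-1(5) asks for willingness to give serum at the set times, and exclusion 5-2(2) removes patients whose serum collection is insufficient, a term the protocol does not define.

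**The concern.** The time origin is the first dose, but the eligibility wording lets entry into the cohort come later. A patient who enters late must have lived to the consent date. Patients who died between first dose and the day they might have been approached never appear. Time from first dose to consent is then death-free by selection, and a Kaplan-Meier curve from first dose that ignores this is too high. The same patients cannot give the pre-treatment sample, so the baseline sNectin-4 value would be missing for them.

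At stake are the absolute OS, PFS and ORR figures, the comparison of EV with chemotherapy if the cohorts differ in late entry, and the completeness of the baseline serum marker. An analysis plan cannot recover patients who died before they could consent, so the matter belongs in the eligibility text.

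**Working it through.** The protocol states no figure to reproduce: the 100 + 100 sample size comes without rates, power or effect size. The check is a reading of the text, followed by an illustration.

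**Text.** Take a patient who began EV three months ago and is approached today. 5-1(3): met. 6-1(1): met if still on EV. 9-3: met if consent is signed before enrolment. 5-1(5): met if willing. 5-2(2): undecided, since later samples might or might not count as sufficient. 8-1(2), first draw: impossible. The treatment and consent rules pass a patient for whom a scheduled sample cannot exist.

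**Absolute outcomes.** All inputs here are assumptions: ORR 45%; exponential OS with median 20 months in responders and 8 in non-responders; a fraction f consents at a delay uniform on 0 to D months and is kept only if alive.

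True survival is S(t) = 0.45·2^(−t/20) + 0.55·2^(−t/8). S(11.7) = 0.30 + 0.20 = 0.50, so the true median is 11.7 months.

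The probability of being kept, for a subgroup with median m, is k(m) = 1 − f + f·[m/(D ln 2)]·(1 − 2^(−D/m)). The overall kept fraction is P = 0.45·k(20) + 0.55·k(8). Observed ORR = 0.45·k(20)/P. For t beyond D, the naive curve is S(t)/P, so the naive median solves S(t) = P/2.

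| | f = 20%, D = 6 | f = 40%, D = 12 |
|---|---|---|
| k(20) | 0.8 + 0.2 × 0.903 = 0.981 | 0.6 + 0.4 × 0.818 = 0.927 |
| k(8) | 0.8 + 0.2 × 0.780 = 0.956 | 0.6 + 0.4 × 0.622 = 0.849 |
| P (lost) | 0.967 (3%) | 0.884 (12%) |
| Observed ORR | 45.6% | 47.2% |
| Naive median OS | 12.3 months (+5%) | 13.9 months (+19%) |

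If every patient enters before the first dose, f = 0, P = 1 and the bias is zero.

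**Between-cohort comparison.** Assume no true difference, one cohort entering uniformly late and the other on time, and follow-up cut at 36 months. With 1,000,000 simulated patients per scenario, the naive Cox hazard ratio is 0.85 (0-4 months late) and 0.79 (0-6 months) for a median of 8 months, and 0.89 and 0.84 for a median of 12. Entering late patients in the risk set at their consent date returns 1.00 in all four.

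**Within-cohort marker association.** With the same delay in both marker groups (0-4 or 0-6 months, median 8), a true hazard ratio of 0.5 reads 0.50.

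For response, suppose ORR is 60% in marker-high and 30% in marker-low patients: odds ratio (0.6/0.4)/(0.3/0.7) = 3.50. If survival depends on the marker only through response, late entry multiplies the odds of response in both marker groups by the same k(20)/k(8), for example 0.927/0.849 = 1.09. The factor cancels and the odds ratio stays 3.50. The cancellation fails if delay differs by marker level or the marker affects survival apart from response.

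**The case against.** The strongest reply is that pre-treatment enrolment is plainly intended. The design is called prospective, patients must be willing to give serum at set times, the first of those times precedes therapy, and insufficient serum is an exclusion. On this reading the word received merely names the treatment cohort. This has force as evidence of intent, and it makes the correction easy. It does not supply a rule. A design label sets no enrolment time, willingness can be given at any point, and without a definition of insufficient, a patient with only the later samples could be kept. Consecutive enrolment does not help either, because it applies to whoever is eligible.

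A second reply is that delayed-entry analysis belongs in the statistical analysis plan, which is not at hand. That stands for the analysis detail, but not for eligibility and consent timing.

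The objection does defeat several stronger readings that a reader might infer:
- *That progression and ORR also carry guaranteed time.* No criterion requires a late entrant to be progression-free. Guaranteed time is strict only for OS and the death part of PFS. For ORR the fault is loss of early deaths from the denominator.
- *That only Group 2 has a calendar limit, so the cohorts are biased differently.* 6-2(1) says "received first-line platinum-based chemotherapy at NTUH during the same enrollment period". The word same points back to a window shared with Group 1, and 4-5 gives one study period. Asymmetry is possible but not shown.
- *That the primary marker association is distorted.* The calculations above leave it essentially unchanged unless the stated exceptions apply.

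**Conclusion.** The point holds as a conflict in an operative eligibility rule. The inclusion, cohort and consent wording permit entry after the first dose; the serum schedule and the prospective label presuppose entry before it.

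To the extent late entry occurs, absolute OS, PFS and ORR are biased upward, and the EV-versus-chemotherapy comparison is biased if late entry differs between the cohorts. In the illustration the shift is small with modest late entry (median OS +5%, ORR +0.6 points) and material for OS with heavy late entry (+19%, ORR +2.2 points). If only one cohort enters late, a null hazard ratio reads about 0.8 to 0.9. These sizes rest on assumed response rates, survival medians, late-entry fractions and delays; the protocol gives none of them. It also gives no evidence that late entry has occurred, so it cannot be said that the outcomes are inflated, only that the text leaves the route open. The change should be made because it is cheap and early deaths cannot be recovered later.

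**What to change.** Reword 5-1(3), 6-1(1) and 6-2(1) so that both groups consist of patients about to start the index regimen (EV/EVP, or first-line platinum). State in 9-3 that consent and enrolment precede the first dose of that regimen. Use the same wording and calendar window for both groups. In 8-1(2), anchor the baseline draw to the index regimen, and in 5-2(2) say whether a missing baseline sample counts as insufficient.

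For any patient already enrolled after starting, record the first-dose and consent dates and enter the patient in the PFS and OS risk sets at the consent date. A patient who progressed before consent then contributes nothing to PFS. Report ORR with and without these patients, since delayed entry does not repair a proportion.

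The cost is a wording amendment, one extra date in the data set, and slightly slower accrual because patients already on treatment can no longer be added.

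### Exclusion 5-2(2) for insufficient serum names no draw, keeps patients with usable tissue out of the serum-free primary analysis, and permits selection on events after treatment start

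*Protocol*

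**What the plan says.** Protocol 5-2(2) lists "Inadequate tissue samples or insufficient serum collection" among the exclusions for the study population. It gives no draw, no minimum number of samples and no time at which sufficiency is judged. Inclusion 5-1(5) separately requires "Willingness to provide serum samples at predefined time points".

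The primary objective (3-1) is "To investigate the correlation between membranous nectin-4 (mNectin-4) expression and treatment outcomes in patients with aUC receiving EV/EV-P". Section 8-1(1) states how that marker is measured: "Tumor samples will be analyzed for mNectin-4 and ADAM10/17 expression by IHC", on archival FFPE specimens. The primary outcome (7-1) is ORR by RECIST 1.1. Under 6-1(3) and 8-1(2), serum serves only the sNectin-4 ELISA, which belongs to a secondary and an exploratory objective.

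Section 8-1(2) schedules three draws: "before the initiation of systemic therapies/at first radiographic response assessment" (the latter at about week 6 to 8), and a third at "disease progression or end of treatment". Section 7-2 counts PFS and OS from the start of treatment.

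On timing of entry, 4-2 calls the design prospective and 9-3 puts consent before enrolment. Inclusion 5-1(3) reads "Received EV/EVP or first-line platinum-based chemotherapy at NTUH", while 6-1(1) describes the EV cohort as "Patients with aUC receiving EV/EVP at NTUH".

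**The concern.** There are two separate problems.

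First, the clause governs membership of the whole study although only one set of analyses needs serum. A patient with evaluable tissue and a known response can be left out of the mNectin-4/ORR analysis for want of a sample that analysis never uses. Sections 4-4 and 5-3 plan consecutive enrolment, and the clause thins that series for a reason unrelated to the primary question.

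Second, two of the three draws fall after the time origin of PFS and OS and after the treatment whose response is being measured. If the clause were applied to either of them, what happens after treatment start would decide who is counted. Patients who die or drop out early would be missing because they did badly. Patients still on treatment, with no third draw yet due, would be missing because they did well.

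**Working it through.** **No figure to reproduce.** The protocol states 100 EV/EVP patients and 100 comparators, with no derivation and no assumed response rate, event rate or dropout. The check is therefore a reading of the sections against each other, followed by illustrations on assumed values.

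**Step 1: what each analysis needs.**

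| Analysis | Tissue | Serum |
|---|---|---|
| mNectin-4 v ORR (3-1, 7-1, 8-1(1)) | yes | no |
| ADAM10/17 v outcomes (3-2(1), 8-1(1)) | yes | no |
| sNectin-4 v outcomes (3-2(2), 8-1(2)) | no | yes |

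The exclusion applies to all three rows, and its serum half is relevant to one.

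**Step 2: which draw.** Willingness is already covered by 5-1(5), so 5-2(2) adds a condition on actual collection. If it is judged at enrolment before the first dose, only the pre-treatment draw can exist and no later event can influence entry. If it is judged later, the week 6 to 8 draw or the third draw could count. The past tense in 5-1(3) does not fix enrolment before the first dose. The text does not choose.

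**Step 3: ORR if a later draw counts.** Assumed true ORR 50%; e is the share of all patients lost.

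- Lost patients all non-responders (early death or dropout): observed ORR = 0.50/(1 − e). For e = 5, 10, 15, 20%: 52.6, 55.6, 58.8, 62.5%.
- Lost patients all responders still on treatment without the third draw: observed ORR = (0.50 − e)/(1 − e). For e = 5, 10, 15%: 47.4, 44.4, 41.2%.

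A milder case takes exponential PFS with an assumed median of 6 months. The share with an event by week 8 (1.84 months) is 1 − 2^(−1.84/6) = 0.191. If 10% to 30% of these leave no later sample and all are non-responders, the loss is 1.9% to 5.7%. ORR then reads 0.50/(1 − loss) = 51.0% to 53.0%. The retained median PFS is 6 × (1 − log2(1 − loss)) = 6.2 to 6.5 months. For comparison, the standard error of an ORR of 50% at n = 100 is √(0.25/100) = 5 points.

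**Step 4: OS if deaths before week 7 are excluded.** Assumed exponential OS; week 7 is 1.61 months. The share removed is 1 − 2^(−1.61/m), and the retained median is m + 1.61. For m = 9, 12, 16 months, 11.7, 8.9, 6.7% are removed and the median reads 10.6, 13.6, 17.6.

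**Step 5: the mNectin-4 association.** Assumed equal halves, ORR 60% (high) v 40% (low), true odds ratio 2.25. With a and b the shares of the high and low groups lost, all non-responders:

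OR = [0.60/(0.40 − a)] / [0.40/(0.60 − b)] = 1.5 × (0.60 − b)/(0.40 − a).

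- a = b = 10%: 1.5 × 0.50/0.30 = 2.50.
- a = 5%, b = 15%: 1.5 × 0.45/0.35 = 1.93.
- a = 5%, b = 20%: 1.5 × 0.40/0.35 = 1.71.
- b = 1.5a: 2.25, unchanged.

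The direction depends on how losses differ between marker groups, which cannot be known in advance.

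**The case against.** The strongest reply is that exclusion criteria are ordinarily judged at enrolment. In a prospective cohort with consent before entry, only the pre-treatment draw can then exist, and a sample due at progression cannot be checked at entry. This stands. A reader might infer that the plan will select on post-treatment events, but the document only leaves that open. The baseline-only reading is plausible and free of such bias.

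The clause might also be meant only for the sNectin-4 analyses, since serum has no other use. That reading would remove the first problem too, so the loss of tissue-evaluable patients is not certain on every possible reading. However, no section states the limit, and the clause stands in the eligibility list. An analysis plan that is not shown could define analysis sets, but it could not recover patients who were never enrolled.

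Requiring both specimens so that all markers rest on the same patients is a legitimate choice, and 3-3 and 7-2(4) do consider the markers together. The protocol does not give this as its reason, and the primary objective does not need it. Willingness under 5-1(5) also narrows the cohort, but it is a condition known at entry and can remain.

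A reader might infer that the primary analysis falls below 100. If serum is judged at entry, excluded patients are not among the 100 and recruitment can continue, so that inference is unsupported.

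Finally, the milder illustration moves ORR by 1 to 3 points, less than its standard error, and early progressors have a third draw scheduled at progression. Both points stand. The larger shifts need a stricter rule or heavier losses.

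**Conclusion.** The point holds in a limited form. As written, 5-2(2) is a study-level exclusion that keeps patients with evaluable tissue and a known response out of a primary analysis that uses no serum. If judged at entry, the cost is to representativeness more than to numbers.

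The wording also permits, without requiring, exclusion for a missing later draw. ORR could then be biased upward by losing early deaths and dropouts, or downward by losing responders still on treatment. The mNectin-4 odds ratio could move either way or not at all.

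The size cannot be derived from the document. The illustrations rest on an assumed ORR of 50% overall (60% v 40% by marker), exponential times, and lost patients being all non-responders or all responders. Under a baseline-only rule the post-treatment distortions are zero. The clause should be corrected, although no bias has been shown to occur.

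**What to change.** Limit the cohort exclusion in 5-2(2) to inadequate tissue. Let a missing serum draw, pre-treatment or later, remove a patient only from the sNectin-4 analyses that need that draw. Add a sentence that every enrolled, treated patient stays in the ORR, PFS and OS analyses whatever later draws are missing.

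If a serum condition is kept for eligibility, tie it to the pre-treatment sample and state that it is judged at enrolment. This removes selection on later events but still keeps some tissue-evaluable patients out. Willingness to give serum in 5-1(5) may stay as an entry condition.

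The cost is one reworded clause and one added sentence. The sNectin-4 analyses would rest on a slightly smaller and slightly different set of patients than the tissue analyses, so the number analysed should be reported for each marker.

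### Does pooling EV monotherapy and EV plus pembrolizumab in one cohort leave the mNectin-4 analysis confounded by regimen or line of therapy?

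*Protocol*

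**What the plan says.** The primary objective (Protocol 3-1) is "To investigate the correlation between membranous nectin-4 (mNectin-4) expression and treatment outcomes in patients with aUC receiving EV/EV-P". Section 5-4 sets one target of 100 patients for this group, with no quota by regimen, and section 6-1(2) gives its treatment as "Standard EV-based regimen (monotherapy or in combination with pembrolizumab". The background (section 2) describes efficacy "both in the first-line setting when combined with pembrolizumab and in later-line setting when used as monotherapy (EV/EVP", so regimen and line tend to go together. Inclusion criterion 5-1(3), "Received EV/EVP or first-line platinum-based chemotherapy at NTUH", restricts line for chemotherapy only.

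The data to be collected (6-1(4)) begin with "Demographics, disease characteristics, treatment details, response assessments (RECIST". For the marker, 8-1(1) says that "tumor specimens will be retrieved from diagnostic pathology samples", and it makes no distinction by regimen.

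The analysis section has three layers. For group comparisons, 8-3(2) lists simple tests, ending with chi-square or Fisher's "exact test for categorical variables". For survival, 8-3(3) gives Kaplan-Meier estimates and "Log-rank test for between-group comparisons". Section 8-3(4), headed as multivariable analysis, assigns a Cox model to the biomarkers' association with survival net of other factors and logistic regression to objective response. No covariate of any kind is listed.

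**The concern.** Treatment is not randomised, and the combination may well have a different response rate from monotherapy. If mNectin-4-high tumours are also more common in one regimen, the marker carries part of the regimen's effect. A marker with no effect could then look predictive, or a real one could be masked, in the analysis the study exists to do. Because 5-1(3) leaves line open for EV, regimen and line could each contribute. The tests named in 8-3(2) and 8-3(3) are unstratified. Section 8-3(4) mentions neither factor and does not say that the logistic model, rather than a simple test, carries the primary question. Naming the two terms would cost only wording, so the gap looks worth closing.

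**Working it through.** The Protocol gives no response rate, marker prevalence, regimen split or error rate, so there is no planned figure to reproduce. Only the cohort size of 100 comes from the document. Everything else below is an assumption.

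**1. How much bias could there be?** Assume:
- an even regimen split;
- ORR of 40% on monotherapy and 65% on the combination;
- no marker effect within either regimen;
- a proportion h_m marker-high on monotherapy and h_c on the combination, with h_m + h_c = 1, so that 50 patients are marker-high and 50 marker-low.

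Then

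- ORR in marker-high: h_m × 0.40 + h_c × 0.65
- ORR in marker-low: (1 − h_m) × 0.40 + (1 − h_c) × 0.65
- difference: (h_c − h_m) × (0.65 − 0.40)

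The spurious difference is the marker gap times the ORR gap, so it vanishes if either is zero.

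| Marker gap | ORR high / low | Odds ratio of a null marker | Rejection at two-sided 5%, normal approximation |
|---|---|---|---|
| 0 points | 52.5% / 52.5% | 1.00 | 5.0% |
| 10 points | 53.75% / 51.25% | 1.11 | 5.7% |
| 20 points | 55% / 50% | 1.22 | 7.9% |
| 40 points | 57.5% / 47.5% | 1.50 | 16.9% |

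For the last row, the odds ratio is (0.575/0.425)/(0.475/0.525) = 1.50. The null standard error is √(0.525 × 0.475 × 2/50) = 0.0999 and the alternative one is √((0.575 × 0.425 + 0.475 × 0.525)/50) = 0.0994. The upper tail is Φ((0.10 − 1.96 × 0.0999)/0.0994) = Φ(−0.964) = 0.168 and the lower tail is 0.001, together 16.9%.

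Simulation of the pooled chi-square (40,000 runs per setting) agrees: 5.5%, 6.2%, 8.5% and 17.9%. With an 80/20 EV/EVP split the figures are 5.3%, 5.5%, 6.4% and 10.4%. With a combination ORR of 50% and an even split they are 5.5%, 5.4%, 5.7% and 7.2%. Stratifying by regimen (Cochran-Mantel-Haenszel) holds 4.6–5.3% throughout.

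**2. The same for PFS.** A Cox model for a null marker with no other term (regimen hazard ratio 0.5–0.8) rejects 5.0–6.2%, 5.5–9.3% and 5.9–22.8% at gaps of 10, 20 and 40 points. With regimen and line included it rejects 5.1–6.2%. At a 10-point gap the two are indistinguishable.

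**3. Do these error rates belong to the planned analysis?** The unadjusted logistic and Cox figures come from models that contain the marker and nothing else, whereas 8-3(4) plans multivariable models. Regimen is the obvious first covariate. If line rather than regimen is the true driver, with a 20–40-point marker gap and 90% of patients in the section 2 pairing, regimen alone brings the logistic model from 5.9–17.0% to 5.3–6.5% and the Cox model from 5.6–22.1% to 5.3–7.8%.

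The chi-square figures apply only if the group comparisons of 8-3(2) mean marker-high against marker-low within the EV cohort. Section 6 uses Group 1 and Group 2 for the EV and chemotherapy cohorts, so that is one reading and not the only one. Section 8-3(2) also allows Fisher's exact test. With the continuity-corrected chi-square as a close proxy (ORR 40% against 50% or 65%, splits 50/50 and 80/20), error is 3.1–5.6% for gaps up to 20 points. It exceeds 7.0% only with a 40-point marker gap, a 25-point ORR gap and an even split together (13.1%).

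**4. Does the Protocol show the necessary imbalance?** No. It reports no difference in mNectin-4 by regimen or line, and 8-1(1) takes diagnostic tissue for everyone. Tissue age and intervening therapy are not limited, so a difference by line is possible, but that is inference.

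**The case for a change.** The best argument for acting is that this is more than an absent covariate list. The Protocol itself builds the heterogeneity in: it pools two regimens that it associates with different lines, makes the pooled group the subject of its primary objective, and seeks a marker association net of other factors. Nothing in an observational design balances the marker across regimens. With 100 patients, naming the terms beforehand would also prevent a later choice between pooled and adjusted results. The loss can be in power as well as in error: if marker-high is 20 points commoner on monotherapy, omitting regimen costs 3–18 points of power for ORR and 4–28 points for PFS under the simulated effects (marker odds ratio 3, marker hazard ratio 0.55).

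The facts in this argument stand, and so does its conditional logic: a marker analysis that omitted regimen would be biased if the marker were unbalanced. What does not follow is that the Protocol plans such an analysis. Pooling in 3-1 and 6-1 defines who is studied, not which terms enter the model. The choice of covariates and of the main model is ordinary content for a statistical analysis plan, which may exist and is not shown. The power losses again compare models with and without regimen. With a balanced marker they shrink to 0–2 points for ORR and 0–6 points for PFS.

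Requiring both terms in the Protocol has a drawback too. If enrolment follows the section 2 pairing completely, regimen and line are the same variable and cannot both be fitted. The simulations cover 90% pairing only. That decision is better made once the regimen-by-line table is known, without looking at outcome.

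**Conclusion.** No change to the plan follows. The Protocol is silent on regimen and line as model terms, but it states nothing wrong and prescribes no unadjusted marker analysis. It plans multivariable models and collects the treatment details they need, and analysts would fill this gap sensibly, with regimen or a combined regimen/line factor.

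The harm, if regimen were nevertheless left out, rests wholly on assumed inputs. It is nil for the ORR error rate when the marker is balanced, about one percentage point or less at a 10-point marker gap, and substantial (17–23%) only at a 40-point gap with a strong regimen effect. Those upper figures belong to analyses without covariates and should not be cited as the error of the models in 8-3(4). The conclusion would change if a statistical analysis plan fixed an unadjusted pooled test as the primary mNectin-4 analysis.
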